7.2. Questionnaire/Scoring

In questionnaires, if multiple responses are provided to a single-response question, the question is deemed as missing.

7.2.1. Modified Neuropathy Impairment Score (mNIS+7) and Original Neuropathy Impairment Score + 7 Nerve Tests (NIS+7)

[figure not shown]
Note: the mNIS+7 and NIS+7 measurements are conducted in duplicate per time point. The average of 2 complete duplicate values will be reported, except in cases of missing or partially missing data as described in the table below.

Assessment Tool	Total Points	Components (maximum points)
Modified NIS+7	304	
 • NIS-W: Weakness (192) • NIS-R: Reflexes (20) • Quantitative sensory testing by body surface area including touch pressure (TP) and heat as pain (HP): QST-BSA_{TP+HP5} (80) • $\sum 5$ nerve conduction studies (10) 
 • Ulnar compound muscle action potential (ulnar CMAP) • Ulnar sensory nerve action potential (ulnar SNAP) • Sural sensory nerve action potential (sural SNAP) • Tibial compound muscle action potential (tibial CMAP) • Peroneal compound muscle action potential (peroneal CMAP) • Postural blood pressure (BP) (2)
NIS+7	270	
 • NIS-W: Weakness (192) • NIS-R: Reflexes (20) • NIS-S: Sensation (32) • $\sum 7$ Nerve tests 
 • 5 Nerve conduction studies $\sum 5$ (18.6) 
 • Peroneal compound muscle action potential (peroneal CMAP) • Peroneal motor nerve conduction velocity (peroneal MNCV) • Peroneal motor nerve distal latency (peroneal MNDL) • Tibial motor DL • Sural sensory nerve action potential (sural SNAP) • Vibration detection threshold (VDT) (3.72) • Heart rate response to deep breathing (HRdb) (3.72)

7.2.1.1. Modified Neuropathy Impairment Score (mNIS+7)

There are 5 components within mNIS+7 total score including NIS-W, NIS-R, QST, $\sum 5$ NC, and postural BP, as described in details below.

1.

[REDACTED]

- [REDACTED]
- [REDACTED]
- [REDACTED]
- [REDACTED]
- [REDACTED]

[REDACTED]

- [REDACTED]
- [REDACTED]
- [REDACTED]
- [REDACTED]

- [REDACTED]

7.2.1.2. Original Neuropathy Impairment Score (NIS+7)

The components of NIS+7 include the following:

1. NIS-W as described in previous section.
2. NIS-R as described in previous section.
3. NIS-S is the sum of the finger and toe sensation components (touch pressure, pin-prick, vibration, joint position). Assessments are performed separately for the right- and left-hand side of the body. Scoring for the sensory assessment is 0 (normal), 1 (decreased) and 2 (absent). The maximum total score for NIS-S is 32.
4. $\sum 7$ nerve tests normal deviates includes the following:
 - $\sum 5$ nerve conductions:
 - For peroneal DL and tibial DL, using normal deviate
 - For peroneal CMAP, peroneal CV and sural SNAP, using $(-1) \times$ normal deviate
 - Vibration detection threshold (VDT): using normal deviate
 - Heart rate response to deep breathing (HRdb): using $(-1) \times$ normal deviate

Each normal deviate ranges from -3.72 to +3.72. The total score is calculated as the mean normal deviates of the non-missing 7 nerve tests and multiply this value by 7. The total score ranges from -26 to +26.

Missing values will be handled as follows:

- Missing items within the 7 nerve tests are handled in step 5 above.
- If a component of NIS+7 (NIS-W, NIS-R, NIS-S, and 7 nerve tests) is missing from replicate A, then impute the component from replicate B \rightarrow recover 2 complete replicate NIS+7 measures A and B.
- If both replicates A and B are incomplete at *different* components, insert A components into B and B components into A as necessary \rightarrow recover 2 complete replicate NIS+7 measures A and B.
- If NIS-W component is missing from both replicates A & B, NIS+7 score is considered as missing. If 1 of the other NIS+7 components (NIS-R, NIS-S, and 7 nerve tests) is missing from both replicates A and B, impute this component as the average of the other patients at this time point who had non-missing data (within study arm).
- If 1 entire NIS+7 replicate is missing, use the singular (other) replicate rather than the average of the 2 in subsequent calculations.
- If no single complete NIS+7 measure can be found or recovered, NIS+7 score is considered as missing.

7.2.1.3. NIS Total Score

NIS total score is the sum of NIS-W, NIS-R, and NIS-S. The handling of missing data is similar as the steps described for mNIS+7. If NIS-W is missing from both replicates, NIS score is considered as missing.

7.2.1.4. Large Fiber Nerve Function

The large fiber nerve function is the sum of the point scores of the following:

- [REDACTED]
- [REDACTED]

[REDACTED] The maximum possible large fiber nerve function score is 52.

The handling of missing data is similar as the steps described for mNIS+7. If QST-BSA_{TP} is missing from both replicates, the large fiber nerve function score is considered as missing.

7.2.1.5. Small Fiber Nerve Function

The small fiber nerve function score is the sum of the point score of the following:

- [REDACTED]

[REDACTED]. The maximum possible small fiber nerve function score is 44.

The handling of missing data is similar as the steps described for mNIS+7. If QST-BSA_{HP5} is missing from both replicates, the small fiber nerve function score is considered as missing.

7.2.1.6. Algorithms for Setting Normal Deviates and Points

For nerve conductions and HRdb tests, raw values are provided by the Mayo Clinic. Each raw value is first converted to a z-score which is then used to set either normal deviate or point score.

[REDACTED]

[REDACTED]	[REDACTED]
[REDACTED]	[REDACTED]
[REDACTED]	[REDACTED]
[REDACTED]	[REDACTED]
[REDACTED]	[REDACTED]
[REDACTED]	[REDACTED]
[REDACTED]	[REDACTED]
[REDACTED]	[REDACTED]
[REDACTED]	[REDACTED]
[REDACTED]	[REDACTED]

[REDACTED]

For a given parameter, the calculated z-score is then compared to 2 lookup tables (see below) using the following procedure to assign the normal deviate score:

1. [REDACTED]
- [REDACTED]
- [REDACTED]
- [REDACTED]
- [REDACTED]

6. [REDACTED]

[REDACTED]

The points for the parameters are calculated as follows:

1. [REDACTED]

[REDACTED]

[REDACTED]	[REDACTED]	[REDACTED]	[REDACTED]	[REDACTED]	[REDACTED]	[REDACTED]	[REDACTED]	[REDACTED]	[REDACTED]	[REDACTED]
[REDACTED]	[REDACTED]	[REDACTED]	[REDACTED]	[REDACTED]	[REDACTED]	[REDACTED]	[REDACTED]	[REDACTED]	[REDACTED]	[REDACTED]
[REDACTED]	[REDACTED]	[REDACTED]	[REDACTED]	[REDACTED]	[REDACTED]	[REDACTED]	[REDACTED]	[REDACTED]	[REDACTED]	[REDACTED]
[REDACTED]	[REDACTED]	[REDACTED]	[REDACTED]	[REDACTED]	[REDACTED]	[REDACTED]	[REDACTED]	[REDACTED]	[REDACTED]	[REDACTED]
[REDACTED]	[REDACTED]	[REDACTED]	[REDACTED]	[REDACTED]	[REDACTED]	[REDACTED]	[REDACTED]	[REDACTED]	[REDACTED]	[REDACTED]
[REDACTED]	[REDACTED]	[REDACTED]	[REDACTED]	[REDACTED]	[REDACTED]	[REDACTED]	[REDACTED]	[REDACTED]	[REDACTED]	[REDACTED]
[REDACTED]	[REDACTED]	[REDACTED]	[REDACTED]	[REDACTED]	[REDACTED]	[REDACTED]	[REDACTED]	[REDACTED]	[REDACTED]	[REDACTED]
[REDACTED]	[REDACTED]	[REDACTED]	[REDACTED]	[REDACTED]	[REDACTED]	[REDACTED]	[REDACTED]	[REDACTED]	[REDACTED]	[REDACTED]
[REDACTED]	[REDACTED]	[REDACTED]	[REDACTED]	[REDACTED]	[REDACTED]	[REDACTED]	[REDACTED]	[REDACTED]	[REDACTED]	[REDACTED]
[REDACTED]	[REDACTED]	[REDACTED]	[REDACTED]	[REDACTED]	[REDACTED]	[REDACTED]	[REDACTED]	[REDACTED]	[REDACTED]	[REDACTED]
[REDACTED]	[REDACTED]	[REDACTED]	[REDACTED]	[REDACTED]	[REDACTED]	[REDACTED]	[REDACTED]	[REDACTED]	[REDACTED]	[REDACTED]
[REDACTED]	[REDACTED]	[REDACTED]	[REDACTED]	[REDACTED]	[REDACTED]	[REDACTED]	[REDACTED]	[REDACTED]	[REDACTED]	[REDACTED]
[REDACTED]	[REDACTED]	[REDACTED]	[REDACTED]	[REDACTED]	[REDACTED]	[REDACTED]	[REDACTED]	[REDACTED]	[REDACTED]	[REDACTED]
[REDACTED]	[REDACTED]	[REDACTED]	[REDACTED]	[REDACTED]	[REDACTED]	[REDACTED]	[REDACTED]	[REDACTED]	[REDACTED]	[REDACTED]
[REDACTED]	[REDACTED]	[REDACTED]	[REDACTED]	[REDACTED]	[REDACTED]	[REDACTED]	[REDACTED]	[REDACTED]	[REDACTED]	[REDACTED]
[REDACTED]	[REDACTED]	[REDACTED]	[REDACTED]	[REDACTED]	[REDACTED]	[REDACTED]	[REDACTED]	[REDACTED]	[REDACTED]	[REDACTED]
[REDACTED]	[REDACTED]	[REDACTED]	[REDACTED]	[REDACTED]	[REDACTED]	[REDACTED]	[REDACTED]	[REDACTED]	[REDACTED]	[REDACTED]
[REDACTED]	[REDACTED]	[REDACTED]	[REDACTED]	[REDACTED]	[REDACTED]	[REDACTED]	[REDACTED]	[REDACTED]	[REDACTED]	[REDACTED]
[REDACTED]	[REDACTED]	[REDACTED]	[REDACTED]	[REDACTED]	[REDACTED]	[REDACTED]	[REDACTED]	[REDACTED]	[REDACTED]	[REDACTED]
[REDACTED]	[REDACTED]	[REDACTED]	[REDACTED]	[REDACTED]	[REDACTED]	[REDACTED]	[REDACTED]	[REDACTED]	[REDACTED]	[REDACTED]
[REDACTED]	[REDACTED]	[REDACTED]	[REDACTED]	[REDACTED]	[REDACTED]	[REDACTED]	[REDACTED]	[REDACTED]	[REDACTED]	[REDACTED]
[REDACTED]	[REDACTED]	[REDACTED]	[REDACTED]	[REDACTED]	[REDACTED]	[REDACTED]	[REDACTED]	[REDACTED]	[REDACTED]	[REDACTED]
[REDACTED]	[REDACTED]	[REDACTED]	[REDACTED]	[REDACTED]	[REDACTED]	[REDACTED]	[REDACTED]	[REDACTED]	[REDACTED]	[REDACTED]

Extended Percentiles Table

Variable	WLOWER	WUPPER	ZLOWER	ZUPPER
HRdb	[REDACTED]	[REDACTED]	[REDACTED]	[REDACTED]
UMAE	[REDACTED]	[REDACTED]	[REDACTED]	[REDACTED]
PMAK	[REDACTED]	[REDACTED]	[REDACTED]	[REDACTED]
PMCVK	[REDACTED]	[REDACTED]	[REDACTED]	[REDACTED]
PMLA	[REDACTED]	[REDACTED]	[REDACTED]	[REDACTED]
TMAK	[REDACTED]	[REDACTED]	[REDACTED]	[REDACTED]
TMLA	[REDACTED]	[REDACTED]	[REDACTED]	[REDACTED]
USAW	[REDACTED]	[REDACTED]	[REDACTED]	[REDACTED]
SSAB	[REDACTED]	[REDACTED]	[REDACTED]	[REDACTED]

7.2.2. Norfolk Quality of Life-Diabetic Neuropathy (QOL-DN)

QOL-DN is a tool for assessing patients' perception of the effects of diabetes and diabetic neuropathy. There are 35 questions divided into 5 domains. The range of possible total scores is -4 to 136.

Part I: Symptoms

[REDACTED]

Part II: Activities of Daily Life

Subscales and Scoring Algorithm

The Total QOL and 5 domains should be summed as follows:

- Total QOL [redacted]
- Physical Functioning/Large Fiber [redacted]
- Activities of Daily Living (ADLs) [redacted]
- Symptoms [redacted]
- Small Fiber [redacted]
- Autonomic [redacted]

The total score and domain scores are calculated without weighting of any kind, and reported as the integer sum of the listed questionnaire items.

Domain scores are calculated as the rounded integer value of the average scores of non-missing included items multiplied by the number of items if at least 50% of the items are non-missing. A domain score is missing if more than 50% of the included items are missing.

If the scores for all 5 domains are non-missing, then Total QOL is the sum of scores of the 5 domains; however, if at least 1 of the domains is missing and at least 50% of the items (18 items) are non-missing, then Total QOL is calculated as 35 times the mean of the non-missing items, rounded to the nearest integer. Otherwise, Total QOL is deemed as missing.

7.2.3. EuroQOL-5-Dimension 5-Level (EQ-5D-5L)

Each of the 5 dimensions (Mobility, Self-Care, Usual Activities, Pain/Discomfort, Anxiety/Depression) is scored on a 5-point Likert scale from 1 (“I have no problems/pain/anxiety”) to 5 (“I am unable to...,” “I have extreme anxiety/depression”).

The 5 scores are concatenated together (in the order of Mobility, Self-Care, Usual Activities, Pain/Discomfort, Anxiety/Depression) to create an EQ-5D-5L profile (e.g., 11111, 55555). The profile is then used to obtain an index value using the United States value set. The index values range from -0.109, associated with a profile of 55555, to 1.0, associated with a profile of 11111. Smaller index values indicate greater impairment.

Missing values are handled as follows:

- Missing items are coded as “9” in creating patient profiles.
- The index value is deemed as missing when responses are missing for 1 or more of the 5 dimensions.
- If the entire instrument is missing, the EQ-5D-5L index value is considered as missing.

7.2.4. Rasch-Built Overall Disability Scale (R-ODS)

The R-ODS consists of 24 items scored on a scale of 0 (unable to perform), 1 (able to perform, but with difficulty) or 2 (able to perform without difficulty). A total score will be calculated as the average of all non-missing items multiplied by 24 if at least 90% of the items are non-missing. The total score will be deemed as missing if more than 10% of the items (3 or more items) are missing.

7.2.5. Composite Autonomic Symptom Score (COMPASS-31)

The COMPASS-31 questionnaire comprises 6 domains: Orthostatic intolerance, Vasomotor, Secretomotor, Gastrointestinal, Bladder, and Pupillomotor. Within each domain, individual questions are scored as follows: Simple yes or no questions are scored as 0 points for no and 1 point for yes. Questions about a specific site of symptoms or symptoms under specific circumstances are scored as 0 if not present and as 1 if present for each site or circumstance. All questions regarding the frequency of symptoms are scored as 0 points for rarely or never, 1 point for occasionally or sometimes, 2 points for frequently or “a lot of the time,” and 3 points for almost always or constantly. All questions regarding the severity of symptoms are scored as 1 point for mild, 2 points for moderate, and 3 points for severe. Questions assessing the time course of a symptom are scored 0 points for responses such as “gotten somewhat better,” “gotten much better,” “completely gone,” and “I have not had any of these symptoms,” 1 point for “stayed about the same,” 2 points for “gotten somewhat worse,” and 3 points for “gotten much worse.” The scores for changes in bodily functions depend on the individual question asked. For example, “I get full a lot more quickly than I used to when eating a meal” is scored 2 points and “I get full a lot less quickly than I used to” is scored 0 points, while the answer “I sweat much more than I used to” is given 1 point and “I sweat much less than I used to” is scored 2 points.

The overall scoring proceeds as follows:

[REDACTED]

[REDACTED]

[REDACTED]

[REDACTED]

[REDACTED]

[REDACTED]

[REDACTED]

[REDACTED]

[REDACTED]

The table content is almost entirely redacted with black boxes. The visible structure suggests a table with at least two columns, separated by a vertical line. The redactions cover all data and text within the table cells.

[Redacted]	[Redacted]
[Redacted]	[Redacted]
[Redacted]	[Redacted]
[Redacted]	[Redacted]
[Redacted]	[Redacted]
[Redacted]	[Redacted]
[Redacted]	[Redacted]
[Redacted]	[Redacted]
[Redacted]	[Redacted]
[Redacted]	[Redacted]
[Redacted]	[Redacted]
[Redacted]	[Redacted]
[Redacted]	[Redacted]
[Redacted]	[Redacted]
[Redacted]	[Redacted]
[Redacted]	[Redacted]
[Redacted]	[Redacted]
[Redacted]	[Redacted]
[Redacted]	[Redacted]
[Redacted]	[Redacted]
[Redacted]	[Redacted]

The table consists of 9 rows and 2 columns. All text within the table is completely redacted with black boxes. The redaction covers the entire content of each cell, leaving only the structural grid lines visible.

[REDACTED]	[REDACTED]	[REDACTED]
[REDACTED]	[REDACTED]	[REDACTED]
[REDACTED]	[REDACTED]	[REDACTED]
[REDACTED]	[REDACTED]	[REDACTED]
[REDACTED]	[REDACTED]	[REDACTED]
[REDACTED]	[REDACTED]	[REDACTED]
[REDACTED]	[REDACTED]	[REDACTED]
[REDACTED]	[REDACTED]	[REDACTED]

5. CHANGES TO PLANNED ANALYSES

The SAP version 2.0 includes more details previously not discussed in the original SAP version 1.0. The following major changes will be implemented in the SAP version 2.0 that are different from the planned analysis specified in the SAP version 1.0 and/or the protocol version 6.0.

This SAP Version 2.1 incorporates an additional change to censor data post alternative treatment for the analysis of NIS-W, which is documented in Section 5.6.

5.1. Primary Analysis Method for Efficacy Endpoints

In the study protocol and the original SAP V1.0, the primary analysis method specified for the primary and secondary efficacy endpoints was the MI/ANCOVA. The original SAP V1.0 was submitted for FDA review (IND Serial # 0019). Following FDA's comment received on 02July2015 and the sponsor's responses on 31August2015, the primary analysis method for all efficacy endpoints will be changed to MMRM method. The history and rationales for the change of primary analysis method are described below. The change is aligned with the CHMP guideline on missing data in confirmatory clinical trials (EMA/CPMP/EWP/1776/99 Rev.1).

Mixed-effects model repeated measures and MI are 2 common methods for handling missing data in analysis of continuous, longitudinal endpoints. For this study, ANCOVA/MI was originally selected as the primary analysis, with MMRM as a key sensitivity analysis.

In the literature, MMRM and MI have been compared in several simulation studies. [Collins et al. \(2001\)](#) noted that the 2 methods yielded similar inference. However, [Barnes et al. \(2008\)](#) found a larger average standard error for MI relative to MMRM, suggesting that MI controls type I error conservatively and loses power to detect true treatment differences. [Siddiqui \(2011\)](#) compared MI/ ANCOVA and MMRM approaches using both simulated datasets and 25 New Drug Application (NDA) datasets of neuropsychiatric drug products, and concluded that MMRM appears to be a better choice in maintaining statistical properties relative to the MI approach when dealing with ignorable missing data.

For the ALN-TTR02-004 trial setting, we compared the properties of these 2 methods via simulation. Our results demonstrated that, while both methods control type I error, MMRM appears to be more powerful in detecting true treatment effect compared with ANCOVA/MI.

Moreover, [White et al. \(2012\)](#) argued that excessive focus on including all randomized patients with missing outcomes can lead to a choice of analysis that rests on implausible or unnecessarily complex imputation. The authors proposed that the main focus in choosing the primary analysis should be the plausibility of its assumptions, while inclusion of all randomized individuals is a requirement only for sensitivity analyses. The MI approach, which includes all randomized patients, is often designated as a sensitivity analysis.

Given these findings – and consideration of the complexity inherent when using the multistep MI approach, the primary analysis method will be changed to MMRM for the primary and secondary efficacy endpoints. MI/ANCOVA will be performed as the key sensitivity analysis for the primary endpoint and for the first secondary endpoint (Norfolk QOL).

5.2. Multiple Imputation/ANCOVA Method

The MI/ANCOVA method, as described in this document and in SAP V1.0, differs from that described in the current clinical protocol (Version 6: September 2015) in the MI method and in the explanatory covariates included in the (complete data) ANCOVA (discussed in Section 5.4).

The MI (for completely missing mNIS+7 assessments) described in the SAP differs from that in the clinical protocol in that 1) stepwise variable selection has been replaced with a pre-specified set of covariates to be included; 2) imputation is done separately by treatment arm. The rationale for these changes is outlined below.

- Stepwise variable selection was removed in order to simplify the analysis.
- The SAP specifies that imputation is done separately by study arm; the current protocol specifies that treatment assignment will not be included in the imputation. This change is motivated by simulations demonstrating a non-negligible loss in power when a single imputation model is employed and treatment is not included in the model; this loss in power is due to “cross-contamination” of imputation models between randomized arms [9].

In the protocol, the number of imputed datasets was specified as 100. In SAP V1.0, the number of imputed datasets was reduced to 10 following the conclusion that 3-5 imputations are often sufficient [10], however, in this SAP V2.0, the number of imputed datasets is increased to 100 to have more precise estimates.

5.3. Hierarchical Testing Order of Secondary Endpoints

In the protocol and SAP version 1.0, it was specified that secondary endpoints would be tested in the following order for the control of overall type I error: Norfolk QOL, NIS-W score, mBMI, 10-meter walk test, and COMPASS-31.

In this SAP amendment, R-ODS has been added as a secondary endpoint for controlled hypothesis testing, and 10-meter walk test has been moved up in the hierarchy. The revised list and order of secondary endpoints is the following: Norfolk QOL, NIS-W, R-ODS, 10-meter walk test, mBMI and COMPASS-31.

These changes were based on the Sponsor’s re-assessment of the clinical importance of these endpoints in hATTR amyloidosis patients.

5.4. Adjustment for Covariates in Statistical Models

The table below summarizes the history of changes in baseline covariates used in the statistical models.

Baseline Covariates	Protocol	SAP V1.0	SAP V2.0
	ANCOVA	ANCOVA	MMRM/ANCOVA
Baseline mNIS+7	X	X	X
Genotype (V30M vs. Non-V30M)	X		X
Genotype class (early onset V30M vs. Other)		X	
Age at hATTR symptom onset (< 50 vs. ≥ 50)			X
Previous tetramer stabilizer use (Yes vs. No)	X	X	X
Region (Western EU, North America, Rest of World)			X
Age at study entry as continuous variable	X		

Genotype class (early onset V30M vs. other) is one of the stratification factors at randomization. The early onset V30M subgroup includes patients who have the V30M genotype and were younger than 50 years old at hATTR amyloidosis symptom onset. At the time of this SAP amendment, the enrollment was complete and there were only 23 early onset V30M patients. Given the small sample size, the composite covariate “genotype class” is decomposed into 2 separate covariates “genotype” and “age at hATTR amyloidosis symptom onset.”

Region is added as a covariate because different rates of attrition and disease worsening were observed for different regions during blinded data monitoring. In addition, adding region may potentially address the influence of different non-V30M types observed across regions.

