9.2.3 Efficacy Analyses

9.2.3.1 Primary Efficacy Endpoint

The primary analysis will compare change in mNIS+7 from baseline between treatment groups of the mITT population. An analysis of covariance (ANCOVA) model, with baseline mNIS+7 value and age as continuous covariates and genotype (V30M vs Non-V30M), prior tetramer stabilizer (tafamidis or diflunisal) use (Yes vs No), and treatment group (patisiran [ALN-TTR02] vs Placebo) as factors will be employed to analyze the primary mNIS+7 endpoint. The mNIS+7 change from baseline will be assessed at 78 weeks. Primary endpoint data that are missing will be inferred using multiple

imputation (MI) (see [Section 9.2.10](#)). Analyses will be conducted using PROC MI and PROC MIANALYZE in SAS 9.2 (or later). The efficacy of patisiran will have been established if the estimate of the parameter associated with treatment variable demonstrates that patisiran improves mNIS+7 relative to placebo with a p-value (2-sided) less than or equal to 0.05, based on the MI methodology.

Sensitivity analyses will assess the robustness of the primary analysis in the mITT and PP populations for different methods of handling missing data, including mixed model repeated measures (MMRM), complete cases (CC), and last observation carried forward (LOCF).

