The estimated worldwide prevalence of FAP is 5,000 to 10,000, with the majority of cases in Portugal, Sweden, France, Japan, Brazil, and the United States [2, 3]. The most common causative mutation of FAP is TTR Val30Met (V30M), with the onset of symptoms typically occurring between 30 and 55 years of age [4]. Amyloid deposition occurs largely in the peripheral nerves, starting as a nerve length-dependent sensory polyneuropathy in the feet causing numbness and pain and progressing to painful dysesthesias. Disabling motor neuropathy follows, characterized by leg weakness and eventually the inability to walk. Autonomic neuropathy is another common feature of the disease, resulting in severe gastrointestinal pathology (including diarrhea or constipation and malabsorption, leading to severe malnutrition), orthostatic hypotension, and bladder dysfunction with recurring urinary tract infections [4, 5, 6, 7]. For several mutations, cardiac pathology also occurs due to amyloid infiltration of the sinus node, atrioventricular conduction system, and infiltration of the myocardium [4, 5]. Involvement of the conduction system can lead to sudden death due to dysrhythmias, and myocardial infiltration can lead to diastolic dysfunction and right-sided heart failure [4]. Cardiomyopathy then proceeds inexorably, leading to death typically within 10 years [4].

Because the liver is the primary source of WT and mutant TTR, orthotopic liver transplantation has been used since 1990 in an attempt to treat FAP [2], and is the current standard of care in patients who are eligible for transplant (patients with minimal neuropathy symptoms and no cardiac involvement). When liver transplantation is performed early in the course of the disease, it can stabilize and slow the course of neuropathic disease in patients with FAP due to V30M, but is less effective in patients with other TTR mutations [2]. However, it is less effective in patients with more advanced disease, especially those with heart involvement, due to the continued production and deposition of WT TTR in tissues with pre-existing amyloid [2, 3, 4].

It is estimated that approximately two-thirds of FAP patients are not transplant-eligible. Furthermore, liver transplant poses risks from the surgical procedure and from life-threatening complications due to graft rejection or infections. The 1-year mortality rate post-transplant is 10% [2].

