4.3.1.1. Primary Analysis using MMRM Method for the mITT Population

The primary analysis will be performed using a restricted maximum likelihood (REML) based MMRM approach. The outcome variable is change from baseline in mNIS+7. The model includes baseline mNIS+7 score as a continuous covariate and fixed effect terms including treatment arm, visit (Month 9 or Month 18), treatment-by-visit interaction, genotype (V30M vs. non-V30M), age at hATTR Symptom onset (< 50 ; ≥ 50), region (North America, Western Europe, and Rest of World), and previous tetramer stabilizer use (yes vs. no). An unstructured covariance structure will be used to model the within-patient errors. The Satterthwaite approximation will be used to estimate the degrees of freedom. The primary comparison is the contrast (difference in least squares means [LS means]) between the patisiran and placebo groups at 18 months. Analysis will be implemented with SAS PROC MIXED.

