4.3.4. Subgroup Analyses

Subgroup analyses will be conducted to assess the consistency of treatment effect within various subgroups defined by the following baseline characteristics:

- Age [≥ 65 ; < 65 at randomization]
- Sex [Male; Female]
- Race [White; Non-White]
- Region [North America; Western Europe; Rest of World]
- NIS [< 50 ; ≥ 50]
- Genotype Class [Early-onset V30M; Other]
- Previous Tetramer Use [Yes; No]
- Genotype [V30M; non-V30M]
- FAP Stage [I; II & III]

Subgroup analyses will be performed for the primary endpoint mNIS+7 and Norfolk QOL-DN using MMRM models with baseline mNIS+7 score as a continuous covariate and genotype (V30M vs. non-V30M) as a factor. A forest plot will be generated to illustrate the estimated treatment effect along with 95% CI within each subgroup.

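### The SAP removes the protocol's continuous age covariate from the primary model without giving a reason; restoring it would cost one degree of freedom and could bring a small gain in precision

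*SAP*

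**What the plan says.** Protocol 9.2.3.1 defines the primary ANCOVA "with baseline mNIS+7 value and age as continuous covariates", with genotype, prior stabilizer use and treatment as factors.

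The SAP 5.4 table traces the covariates from the protocol through SAP V1.0 to V2.0. The row "Age at study entry as continuous variable" is marked in the protocol column and blank in both SAP columns. SAP section 5 says that V2.1 adds only the NIS-W censoring change, so the V2.0 column still applies.

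The text under the table gives two explanations:

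- Because "there were only 23 early onset V30M patients", "the composite covariate “genotype class” is decomposed into 2 separate covariates “genotype” and “age at hATTR amyloidosis symptom onset".
- Region was added because attrition and worsening differed between regions.

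It does not mention age at study entry.

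The age term that remains in the primary MMRM (SAP 4.3.1.1) is "age at hATTR Symptom onset (< 50 ; ≥ 50". The MI/ANCOVA and pattern-mixture ANCOVAs (SAP 4.3.1.3) use the same two-category factor. Age at randomization otherwise appears as a baseline summary (SAP 4.2) and as the mNIS+7 and Norfolk QOL-DN subgroup "Age [≥ 65 ; < 65 at randomization" (SAP 4.3.4).

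**The concern.** SAP 1.1.2 undertakes to set out differences from the protocol. Between the protocol and V2.0 the table shows three net covariate changes: onset age added, region added, age at study entry removed. The first two are explained and the third is not. The reason given for the onset factor, the small early onset V30M group, concerns splitting a stratification composite. It has no bearing on a separate continuous term that was already absent from V1.0.

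The trial enrols ages 18 to 85. With only an onset cut at 50, the model treats everyone within each half alike. If age is related to progression within those halves, the variance that it could explain stays in the residual, and chance age differences between arms within a half go unadjusted. What is at stake is the standard error of the primary contrast and of the two sensitivity ANCOVAs that share the factor.

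**Working it through.** **Inputs from the documents.** SAP 3.1: difference 8.95, SD 16, two-sided alpha 0.05, power 90%, 154 evaluable patients, 25% discontinuation, about 200 enrolled. SAP 1.2.2: 2:1 allocation.

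**Inputs that the documents do not give.** The distribution of onset or entry age, the share of patients with onset below 50, and the strength of the link between age and mNIS+7 change. The 23 patients in SAP 5.4 are early onset V30M only, not everyone with onset below 50. SAP 1.1.1 says only that V30M disease presents "with the onset of symptoms typically occurring between 30 and 55 years of age". Everything from step 2 onward is therefore an illustration.

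**Step 1: the plan's own figure.**

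- Normal approximation: total N = 4.5 × [16 × (1.960 + 1.282) / 8.95]² = 151.1. Rounding each arm up gives 51 + 102 = 153.
- Noncentral t, 2:1: power 0.8999 at 153 and 0.902 at 154, so 154 is reproduced.
- 154 / 0.75 = 205.3, or 206, which agrees with about 200.

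This is a plain two-sample t-test without covariates, so planned power never relied on age.

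**Step 2: share of a linear age effect kept by a two-category split.** For a normal variable with proportion p below the cut c (in SD units), the share kept is k = φ(c)² / [p(1 − p)].

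- p = 0.5: 0.3989² / 0.25 = 0.637
- p = 0.3 or 0.7: 0.3477² / 0.21 = 0.576
- p = 0.2: 0.2800² / 0.16 = 0.490

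Over 20 to 70% below the cut, k runs from 0.490 to 0.637.

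**Step 3: effect on the treatment estimate.** Let R² be the share of outcome variance that continuous onset age would explain (assumed). The variance with the split, relative to the variance with the continuous term, is (1 − kR²) / (1 − R²). Power uses N = 154 and residual SD 16√(1 − R²) or 16√(1 − kR²).

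| R² (assumed) | Variance ratio | Power, continuous | Power, two categories | Difference (points) |
|---|---|---|---|---|
| 0.02 | 1.007 to 1.010 | 0.907 | 0.905 to 0.904 | 0.2 to 0.3 |
| 0.05 | 1.019 to 1.027 | 0.916 | 0.911 to 0.909 | 0.5 to 0.7 |
| 0.10 | 1.040 to 1.057 | 0.929 | 0.919 to 0.915 | 1.0 to 1.4 |

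**Step 4: the covariate actually removed.** The term dropped is age at study entry, not onset age. If the two correlate at r and are jointly normal, the onset split keeps r²k of the entry-age effect. With r from 0.8 to 0.95 (assumed) that is 0.64 × 0.490 = 0.314 to 0.9025 × 0.637 = 0.575. The variance ratios become 1.009 to 1.014, 1.022 to 1.036 and 1.047 to 1.076 for R² of 0.02, 0.05 and 0.10, and the power differences run from 0.2 to 1.8 points. The order of magnitude does not change.

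**Step 5: price of the extra term.** A covariate unrelated to outcome inflates the variance of the treatment estimate by about 1/(N − 4) on average, here 1/150 = 0.7%. At R² = 0.02 this cancels most or all of the gain in step 3 for onset age. At 0.05 and 0.10 a net gain remains.

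**The case against.** The strongest reply is that the change is open, early and minor. The table shows the removal plainly. Age was already absent from SAP V1.0, submitted in April 2015. The protocol synopsis speaks only of adjusting for the stratification factors. The cut at 50 comes from one of those factors, and V2.0 adds an onset-age term that neither the protocol nor V1.0 had. Choosing covariates for a prespecified model is a matter of judgement. All of this stands, except that a visible removal is still not an explained one.

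Three stronger readings are tempting, and the documents do not support them.

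- **That the SAP throws away 36 to 51% of the information in onset age.** A reader could get this from step 2 as 1 − k. It is not a property of this trial. Continuous onset age was never planned, so nothing of it is lost against the protocol. The figure also moves with assumptions that the documents cannot settle: 57 to 66% lost if only 15 to 10% of patients fall below the cut, 25 to 28% for a uniform distribution split at 50 or 40%, 18 to 26% for an illustrative two-peaked distribution, and nothing if the true effect is a step at 50. It is in any case a share of age's own contribution, which may be small, and it ignores overlap with baseline mNIS+7, genotype, region and stabilizer use.
- **That the treatment contrast is biased or type I error inflated.** Under randomisation, omitting or coarsening a baseline covariate costs precision only. Age could also bear on the missing-at-random assumption if it predicts dropout, but the documents give no evidence on that.
- **That the removal was driven by results.** Its absence from V1.0 and the blinded status of the study argue against this.

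**Conclusion.** The point holds as a low-severity improvement. A continuous age covariate named in the protocol's primary model was removed without a stated reason, and the only age term left in the primary MMRM and the two complete-data ANCOVAs is a two-category onset factor. The likely cost is small: for onset age, a variance about 0.7 to 5.7% larger and 0.2 to 1.4 points of power, for an assumed R² of 0.02 to 0.10. This rests on normal age, a linear effect, 20 to 70% of patients with onset below 50, and no overlap with the other covariates, none of which the documents establish. If age explains only about 2% of the variance, the net gain is close to nil. Neither the validity of the primary test nor its planned 90% power is in question.

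**What to change.** Before unblinding, restore age at study entry as a continuous covariate in the SAP 4.3.1.1 MMRM and in the MI/ANCOVA and pattern-mixture ANCOVAs of SAP 4.3.1.3. Keep the onset factor (<50 vs ≥50) beside it, since that cut belongs to the stratification. Add a sentence to SAP 5.4 recording the decision. If the sponsor prefers to leave the primary model as it is, SAP 5.4 should say why age at study entry was removed, and a sensitivity MMRM with continuous age should be prespecified.

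SAP 4.3.1.3 and Appendix 7.1 should also state whether age at onset enters the imputation models as a continuous or a two-category variable; the text does not say.

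The cost is one degree of freedom and a line of text per model. No new data are needed, because age is already summarised at baseline under SAP 4.2.
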